1. Overview. This will be a prospective, longitudinal cohort study designed to include all symptomatic episodes of URI occurring in children between the ages of 49 and 84 months for a period of one year to determine relationships between bacterial colonization of the nasopharynx, acute viral URIs, and acute bacterial sinusitis. To accomplish this goal we will enroll approximately 355 children, ages 49 to 84 months, over a 40 month period (~9 children/month); with an expected attrition rate of 15% this will yield ~ 300 children. Nasal washes (for virus identification) and nasopharyngeal swabs (for nasopharyngeal bacterial culture and microbiota profiling) will be obtained at entry, and surveillance of both sites will be performed on four other occasions (February, April, September and December) throughout the one-year study. In addition, when acute upper respiratory symptoms develop, we will obtain nasal washes and nasopharyngeal swabs during the acute illness and again 1-2 weeks later during the period of spontaneous recovery or when the patient is diagnosed to have acute sinusitis. These samples will be obtained to identify infecting viruses and also to characterize the changes in bacterial microbiota associated with an acute URI and recovery versus an acute URI followed by a secondary bacterial sinus infection. The bacterial assemblages will be characterized using both standard bacteriologic techniques (which will allow semi-quantitation of recognized sinopathogens) and a high-density microarray (16S rRNA PhyloChip) in parallel with high-throughput 454-pyrosequencing (to validate array findings) to comprehensively describe the nasopharyngeal microbiome. Respiratory viruses will be identified from nasal washes using a molecular diagnostic system that can detect all common respiratory viruses (Respiratory MultiCode Assay, EraGen Biosciences).

Figure 2. Overview for Study Participant

Aim 1: To determine the incidence of acute bacterial sinusitis in children ≥ 4 through < 8 years of age (which is the peak age incidence of sinusitis) as a complication of an antecedent viral URI.

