- We will enroll and follow eligible children between ≥ 4 through < 8 years of age prospectively for one year. Using high-throughput multiplex PCR-based viral diagnostics, the identities of antecedent viral infections will be determined for each symptomatic URI, and during four surveillance periods. We hypothesize that rhinovirus will be the most common viral URI to predispose to acute bacterial sinusitis. This information can potentially direct the development of antiviral medication or viral vaccines.
- Using stringent clinical definitions for acute bacterial sinusitis, we will determine the incidence of sinusitis as a complication of viral URI. This has not been previously determined

and we hypothesize that sinusitis will complicate viral URI in 8% of cases in these young children.

Aim 2: To define relationships between the nasopharyngeal microbiome, viral illnesses, and progression to clinical sinusitis.

Nasopharyngeal samples and a pilot number of stool samples obtained before, during and after viral respiratory infections will be analyzed for bacterial species using array-based diagnostics (PhyloChip) and conventional semi-quantitative microbiologic techniques in two groups of children:

- a) those with viral URIs that resolve spontaneously and
- b) those whose URI progresses to acute bacterial sinusitis.

We hypothesize that the presence and density of sinopathogens and inhibitory commensal microbiota, together with modifications caused by infection with common respiratory viruses, will influence the likelihood of progression to acute bacterial sinusitis. Knowledge of these predictive elements will direct preventive strategies and treatment decisions.

The primary objectives of the study are as follows:

1. To determine a) the incidence of acute bacterial sinusitis in children ≥ 4 through < 8 years of age as a complication of an antecedent viral URI, b) if certain viruses are more likely than others to precipitate an episode of bacterial sinusitis and c) what percentage of sinus infections are, in fact, preceded by viral infection.

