2. To compare children who develop acute bacterial sinusitis to children who recover spontaneously with regard to the characteristics of the nasopharyngeal microbiome (both gross features of community composition e.g. diversity, as well as the relative abundance of specific taxa). These comparisons will include samples obtained during the most recent surveillance visit, samples obtained during the acute URI and samples obtained when either a sinus infection has been confirmed or the subject has recovered spontaneously.

The secondary objective of the stool sample sub-studies are:

1. To determine the relationship, if any, between changes that occur in the nasopharyngeal microbiome and the fecal microbiome in the sub-cohort of subjects, and in the index subject and household family members, over time and with respiratory infections.

2. Timeline for conduct of study: There was a 3 month run-in period for IRB approval and training of personnel. The goal is to enroll nine patients per month (over 40 months). Each patient will be followed for 12 months; final follow-up will be completed at month 55. Enrollment began in February, 2012 and is ongoing. To date, 242 subjects have been enrolled. The average enrolled per month is approximately 6.5.

Table 2. Timeline for Conduct of Study

	Year 1				Year 2				Year 3				Year 4				Year 5			
	Quarter				Quarter				Quarter				Quarter				Quarter			
	1	2	3	4	1	2	3	4	1	2	3	4	1	2	3	4	1	2	3	4
Protocol finalization	X																			
Obtain IRB approval	X																			
Hire and train personnel	X																			
Recruitment (n=360)		27	27	27	27	27	27	27	27	27	27	27	27	27	27	27	9			
Analysis																		X	X	X

3. Eligibility and enrollment:

Main Study: Children will be eligible to join this study if they are between ≥ 4 through < 8 years of age and are otherwise healthy (without upper respiratory symptoms to obtain baseline nose samples). Exclusion criteria include underlying conditions which would predispose them to the development of sinusitis including congenital or acquired immunodeficiencies, craniofacial abnormalities, cystic fibrosis, allergic rhinitis or a previous episode of chronic sinusitis. Children will be recruited from four large pediatric practices. Informed consent will be obtained from a parent or legal guardian. Enrollment is ongoing and may extend further than the initial proposed timeline.

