These characteristic clinical presentations that are most likely associated with a bacterial rather than viral infection were adopted and endorsed by a consensus panel in 2003, jointly established by 5 national societies (the American Academy of Allergy, Asthma and Immunology, the American Academy of Otolaryngic Allergy, the American Academy of Otolaryngology – Head and Neck Surgery, The American College of Allergy, Asthma, and Immunology, and the American Rhinologic Society).¹⁷ These clinical definitions for acute sinusitis have now been adopted by the American Academy of Pediatrics and the Infectious Disease Society of America and will appear in both guidelines, which are currently in press. (The PI is an author of both guidelines). In four clinical studies it has been shown that by using these stringent criteria, sinusitis is diagnosed in only 7-8% of respiratory infections presenting to the practitioner who cares for children.^{3,4,6,7}

If a child meets criteria for the definition of sinusitis an additional nasal wash and nasopharyngeal swab will be obtained to identify virus and perform both PhyloChip and conventional culture at that time. A nasal wash and nasopharyngeal swab will also be obtained from children who have recovered spontaneously 10 -14 days after symptoms began. These “recovery” samples will provide information about changes in bacterial community composition that occur following perturbation by viral infection, and will serve as an important comparator to samples obtained during acute sinus infections. Families may choose to have their child seen by the primary pediatrician and if sinusitis is diagnosed the pediatrician may treat with an appropriate antibiotic (standard of care visit). Clinical progress will be tracked until the patient experiences resolution of symptoms.

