Study personnel will send a weekly text to the parent to determine whether there are any URI symptoms have occurred in the last 7 days. The text message will read, “Please call the research staff if your child has had a cough, runny nose, or stuffy nose in the last 7 days. [contact]. Do not respond to this text.” A weekly phone call can take the place of the text message based on parent preference. All subjects included in the study receive their primary and emergency care through the University of Wisconsin Hospital and Clinics. Urgent or immediate care clinics and an “after hours” clinic use the same electronic medical record as does the primary care provider. Thus review of the medical record will permit identification of any episode of sinusitis, URI or other illness for which medical care was sought. Families who are non-responsive after 2 months of follow-up phone calls will be mailed a letter attempting to reconnect with the family and to ascertain whether they wish to continue in the study. A follow-up phone call after 1 week of the mailed letter will be made if we have not heard back from the family.

The family will be mailed a quarterly newsletter that will contain information on colds/sinusitis and an activity for the child. It will also contain a message to call the research staff whenever upper respiratory symptoms are present.

The identity of the viral infection and characteristics of the bacterial colonization of children with an uncomplicated viral URI will be compared to baseline and compared to children whose URI progresses to acute bacterial sinusitis.

Subjects participating in the stool sample collection part of the study will be given instructions and a stool collection kit to take home, collect the sample, and bring to the research staff at the next visit (within 2 days) or the research staff will pick up during a home visit.

d) Study methods – Stool Collection Sub-studies

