To estimate the incidence of acute bacterial sinusitis as a complication of URI we will use a random effects generalized linear model assuming binomial distribution. We expect a total of 1500-1800 episodes of URI among the children and hypothesize that ABS will complicate 8% of these cases resulting in approximately 120 cases of acute bacterial sinusitis. If the true percent of viral URIs progressing to acute bacterial sinusitis is 8% then 1500 cases will give us 80% power to estimate the incidence with a 95% confidence interval no longer than 2.9%. If we were to observe exactly the 8% incidence the 95% confidence interval would be (6.68%, 9.49%).

Aim 2 - The episodes of acute bacterial sinusitis and uncomplicated URI chosen for PhyloChip analysis will be from two groups. The “acute bacterial sinusitis group” will consist of the first episode of acute bacterial sinusitis occurring among 50 randomly selected children who have one or more episodes of acute bacterial sinusitis. Only the first episode will be eligible to avoid data clustered within child. To avoid running all the PhyloChip analysis at the end of the study we will select the children in groups of 10 evenly spaced over the 52-months of enrollment and follow-up. An additional 50 matched control cases of uncomplicated URI will be selected (10 at a time) from the group of children who have not yet had an episode of acute bacterial sinusitis. The controls will be chosen so that their uncomplicated URI closely matches the case of acute bacterial sinusitis in calendar time. If a control child later develops acute bacterial sinusitis, the control child will become eligible to be chosen for the acute bacterial sinusitis group. If this occurs a different matched control will be chosen as a replacement. This process will result in a few extra PhyloChips being run but is necessary as the processing of PhyloChips is time consuming and cannot be delayed until the end of the study. In addition, the surveillance sample most closely preceding the episode of acute bacterial sinusitis and uncomplicated URI will also be analyzed using the PhyloChip.

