Regression analyses will be used to assess relationships between progression to acute bacterial sinusitis, demographic variables (including age, gender, attendance at daycare, family or personal history of asthma, pets, etc.), season and gross metrics of bacterial community composition (richness, evenness, and diversity indices) as well as the relative abundance of all taxa detected (including sinopathogens), to determine if these variables are related to specific features of the nasopharyngeal microbiota. A term will be included to account for the paired structure of the data. For each of the continuous predictors, a difference in the mean values between the acute bacterial sinusitis group and the control group equal to 50% of the variability of that predictor will give us greater than 80% power to find a significant effect of the predictor. For predictors which take values of yes or no (such as presence of a sinopathogen), we will have 80% power to detect the difference between the percent of sinopathogens present equal to 55% for the acute bacterial sinusitis group and 30% for the control group.

PhyloChip outcomes including richness, evenness and diversity indices of the nasopharyngeal microbiome sample obtained during each of the 50 episodes of acute bacterial sinusitis will be compared to those obtained during the most recent surveillance period by using paired t-tests. Differences in specific taxon abundance in these two samples will be determined by paired t-test and adjusted for false discovery.

Correlation analysis of the abundance of each individual taxon against that of key sinonasal pathogens (both bacterial and viral) will also be performed to determine relationships between these species and relative abundance of all other taxa detected. Hierarchical cluster analysis will be used to display similarity of microbiota among nasopharyngeal samples.

The pilot stool sample size is based on the base sample size of 12 per group when no prior information is available (Julious, 2005). We propose to double that number to ensure enough samples over the seasonality of the one year enrollment. This feasibility is based on our average enrollment of 7 subjects per month and if 20% join the sub-study (1-2 per month), enrollment would take about 12 months including family members.

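### Aim 2 names a test of change from surveillance only for the 50 sinusitis episodes; adding the case-control difference in change would use control arrays already planned

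*Protocol*

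**What the plan says.** Data Analysis, Aim 2 (Protocol section i) selects the first sinusitis episode of 50 children and 50 uncomplicated URIs matched to them in calendar time. For both groups, "the surveillance sample most closely preceding the episode of acute bacterial sinusitis and uncomplicated URI will also be analyzed using the PhyloChip".

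The only named test of change from surveillance concerns cases: richness, evenness and diversity from each of "the 50 episodes of acute bacterial sinusitis will be compared to those obtained during the most recent surveillance period by using paired t-tests". Taxa follow the same scheme: "Differences in specific taxon abundance in these two samples will be determined by paired t-test and adjusted for false discovery".

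Elsewhere the question is comparative:
- Overview: samples are taken to "characterize the changes in bacterial microbiota associated with an acute URI and recovery versus an acute URI followed by a secondary bacterial sinus infection".
- Aim 2 hypothesis: sinopathogens and commensals, "together with modifications caused by infection with common respiratory viruses, will influence the likelihood of progression to acute bacterial sinusitis".
- Study procedures, c) Acute respiratory illness: recovery samples "will provide information about changes in bacterial community composition that occur following perturbation by viral infection, and will serve as an important comparator" for the sinusitis samples, and uncomplicated URIs "will be compared to baseline and compared to children whose URI progresses to acute bacterial sinusitis".
- Primary objective 2: the case-control comparisons cover surveillance samples, acute URI samples and "samples obtained when either a sinus infection has been confirmed or the subject has recovered spontaneously".

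The Aim 2 regression relates progression to community indices and taxa and includes a term for pairing. It does not say whether change from surveillance enters, or which pairing is meant.

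**The concern.** A before-after test in cases alone has no control for what happens to any child with a cold, or for the calendar. The scheduled surveillance months are February, April, September and December, so the gaps between rounds are 2, 5, 3 and 2 months and the baseline sample can come from another season. The Protocol itself lists season and recent illness among the sources of variability in colonization (Existing Challenges, b).

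The planned comparisons of level at each visit do not fill the gap. They can show that a group difference already existed at surveillance, but they do not test whether it grew. At stake is whether a reported microbiome change can be linked to progression, which is what Aim 2 asks.

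**Working it through.** The Protocol gives no power or sample size for the paired test, so there is no stated figure to reproduce. The calculations below are illustrations.

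**Inputs.** From the Protocol: 50 cases and 50 controls; two-tailed testing (section e); 0.5 SD as the Aim 2 case-control effect. Assumed: alpha 0.05 for the indices (the Protocol states 0.05 for taxa); SD of an index = 1 at each visit; within-child correlation r = 0, 0.3 or 0.5; the shifts shown.

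**SD of change** = sqrt(2(1 − r)) = 1.414, 1.183, 1.000.

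**1. Within-case test when sinusitis adds nothing.** Noncentral paired t, 49 df, noncentrality = (shift / SD of change) × sqrt(50). For a 0.4 SD shift common to every URI this is 2.00, 2.39, 2.83, so the test is significant in 50%, 65%, 79% of studies. For a 0.2 SD shift: 17%, 22%, 28%.

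**2. Case-control difference in change, same setting.** If controls carry the same shift, the true difference is 0 and the test is significant in about 5%.

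**3. The same contrast when recovered controls have lost the shift.** Recovery samples are taken 10–14 days after onset, from children who are well, while cases are still symptomatic. With the 0.4 SD shift kept in cases and gone in controls, noncentrality = (0.4 / SD of change) × sqrt(50/2) = 1.41, 1.69, 2.00 on 98 df. The contrast is significant in 29%, 39%, 51% of studies with no added sinusitis effect. If the shift has half resolved (difference 0.2 SD): 11%, 13%, 17%.

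**4. A gap at surveillance that merely persists (0.5 SD).** The level comparison at the episode is significant in about 70% of studies and the change contrast in about 5%. A model adjusted for the surveillance value estimates (1 − r) × 0.5 and is significant in 66%, 42%, 28% (simulation, 20,000 studies per setting).

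**5. A true added effect of 0.5 SD with no gap at surveillance.** Power is 42%, 55%, 70% for the change contrast; 70% for levels; 70%, 74%, 82% for the adjusted model.

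**6. Detectable difference at 80% power.**

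| Test | SD of change | SD of level at r = 0, 0.3, 0.5 |
|---|---|---|
| Within 50 cases | 0.40 | 0.57, 0.48, 0.40 |
| Difference in change, 50 v 50 | 0.57 | 0.80, 0.67, 0.57 |

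**7. Why not simply a second paired t-test in controls.** If both groups change equally and each test independently has 80% power, exactly one is significant in 2 × 0.8 × 0.2 = 32% of studies. The difference must be tested directly.

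**The case against.** The strongest reply is that nothing here is an error. The within-case test is valid for what it describes, and naming tests is often left to an analysis plan that is not at hand. Much of this stands. A reader might infer that the 50% to 79% figures are false positives; they are not, because in that setting the microbiome really changed and the Protocol does not claim that the paired test isolates sinusitis. A reader might also infer that controls are never set against baseline, but the acute-illness procedures commit to that comparison and objective 2 includes surveillance samples. The regression's inputs are unspecified; they are not shown to omit change.

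The reply does not dispose of the point. The Protocol does fix a method here, and fixes it for cases alone, while planning the control arrays that would make it comparative. The stated comparisons with baseline and by level do not name a test of the difference in change.

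A second objection also stands in part. It is tempting to say that the matched controls would cleanly isolate a sinusitis effect. Step 3 shows that they do not at the second illness sample. Season is also only partly removed: matching is on the date of the episode, not of the surveillance sample, and the entry specimen can serve as baseline, so the two members of a pair may have baselines from different dates.

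Finally, the change contrast has less power than the level comparison at r = 0 and 0.3, and no more at r = 0.5, when groups start equal. That is a fair reason to add it beside the level comparisons, not in their place.

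**Conclusion.** The point holds as a low-cost improvement that should be made. The named before-after test covers cases only and cannot by itself tell a sinusitis-related change from that of any URI or of season. The arrays needed for a controlled comparison are already foreseen in both groups.

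The size depends on assumed values of r and of the URI shift, since the Protocol gives neither: 50% to 79% significant within cases for a 0.4 SD shift common to all URIs, and 17% to 28% for 0.2 SD. The roughly 5% for the difference in change requires that controls carry the same shift. That is most plausible at the acute visit, on day 3 to 4 of illness, when the groups are at a similar stage. At the second illness sample the contrast compares sinusitis with a recovered state and should not be read as a sinusitis effect net of URI.

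**What to change.** In Data Analysis, Aim 2:

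- Add a test of the case-control difference in change from surveillance: a group-by-time contrast with the matched-pair term, for richness, evenness and diversity, and for taxa with false discovery control.
- Make surveillance to acute URI the main contrast.
- Report surveillance to sinusitis/recovery as secondary, interpreted as sinusitis versus recovered state.
- Include the date or season of the surveillance sample, or its interval to the episode, as a covariate.
- Keep the within-case paired t-test and label it descriptive.
- Optionally report a model adjusted for the surveillance value as support. State beforehand that it asks whether children with the same surveillance value differ at the episode, whereas the contrast asks whether the groups changed differently.

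Cost: no new samples, and no arrays beyond those that objective 2 and Data Analysis, Aim 2 imply. There are more model fits and more false discovery families, across up to about 8,500 taxa. The detectable difference at 80% power is larger, about 0.57 SD of change between groups against 0.40 SD within cases.
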